### 8.2. Method of detecting AE and SAE

Care will be taken not to introduce bias when detecting AE and/or SAE. Open-ended and non-leading verbal questioning of the participant is the preferred method to inquire about AE occurrence.

### 8.3. Follow-up of AE and SAE

After the initial AE/SAE report, the investigator is required to proactively follow each participant at subsequent visits/contacts. All SAEs and AEs (as defined in [Appendix 4](#)), will be followed until resolution, stabilization, until the event is otherwise explained, or the participant is lost to follow-up (as defined in [Section 6.11](#)). Further information on follow-up procedures is given in [Appendix 4](#).

### **8.3.1. Regulatory reporting requirements for SAE**

- Prompt notification by the investigator to the sponsor of an SAE is essential so that legal obligations and ethical responsibilities towards the safety of participants and the safety of a study treatment under clinical investigation are met.
- The sponsor has a legal responsibility to notify both the local regulatory authority and other regulatory agencies about the safety of a study treatment under clinical investigation.
- The sponsor will comply with country-specific regulatory requirements relating to safety reporting to the regulatory authority (IRB)/IEC, and investigators.
- Investigator safety reports must be prepared for suspected unexpected serious adverse reactions (SUSAR) according to local regulatory requirements and sponsor policy and forwarded to investigators, as necessary.
- An investigator who receives an investigator safety report describing an SAE or other specific safety information (eg, summary or listing of SAEs) from the sponsor will file it along with the Investigator's Brochure and will notify the IRB/IEC, if appropriate according to local requirements.

### **8.3.2. Pregnancy**

- Details of all pregnancies in female participants and, if indicated, female partners of male participants will be collected after the start of study treatment and until [REDACTED] after the last dose.
- If a pregnancy is reported, the investigator should inform [REDACTED] Medical Monitor and Aviceda within [REDACTED] of learning of the pregnancy and should follow the procedures outlined in [Appendix 5](#).
- Abnormal pregnancy outcomes (e.g., spontaneous abortion, fetal death, stillbirth, congenital anomalies, ectopic pregnancy) are considered SAE.

## **8.4. Treatment of overdose**

N/A

## **8.5. Safety**

### **8.5.1. General**

Participants will be monitored for any safety and tolerability issues affecting any system.

Any significant abnormality in the opinion of the investigator noted on systemic values obtained from the clinical laboratory testing should be reported as possible adverse events. If there is any question that these represent serious abnormalities, both the medical monitor and sponsor should be notified.

### **8.5.2. Visual safety**

For issues affecting vision. The following are guidelines for reporting the possible adverse events:

- [REDACTED]

### **8.5.3. Physical examinations**

- A physical examination will include, at a minimum, assessments of appearance, mood, and affect. Height and weight will also be measured and recorded at screening.
- A brief physical examination will include, at a minimum, assessments of appearance, mood, and affect and symptoms.
- Investigators should pay special attention to clinical signs related to previous serious illnesses.

### **8.5.4. Vital signs**

- Blood pressure and pulse measurements will be assessed with a completely automated device. Manual techniques will be used only if an automated device is not available.
- Blood pressure and pulse measurements should be taken before blood collection for laboratory tests and after the participant has been sitting for 5 minutes. Repeat testing can be done if needed by the Investigator.

### **8.5.5. Clinical safety laboratory assessments**

Any significant abnormality noted in systemic values obtained from the clinical laboratory testing (central laboratory) should be reported as possible adverse events. If there is any question that these represent serious abnormalities, both the medical monitor and sponsor should be notified.

- Refer to [Appendix 2](#) for the list of clinical laboratory tests to be performed and to the SoA for the timing and frequency.
- The investigator must review the laboratory report, document this review, and record any clinically relevant changes occurring during the study in the AE section of the CRF. The laboratory reports must be filed with the source documents. Clinically significant abnormal laboratory findings are those which are not associated with the underlying disease, unless judged by the investigator to be more severe than expected for the participant's condition.
- All laboratory tests with values considered clinically significantly abnormal during participation in the study or within [REDACTED] after the last dose of study treatment should be repeated until the values return to normal or baseline. If such values do not return to normal/baseline within a period judged reasonable by the investigator, the etiology should be identified, and the sponsor notified.
- All protocol-required laboratory assessments, as defined in [Appendix 2](#), must be conducted in accordance with the laboratory manual and the SoA.
- If there is an urgent need and laboratory values from a non-protocol specified laboratory assessments performed at the institution's local laboratory require a change in participant management or are considered clinically significant by the investigator (eg, SAE or AE or dose modification), then the results must be recorded in the eCRF.

**8.6. Health economics or medical resource utilization and health economics**

9.

For more information, contact the Office of the Vice President for Research and Economic Development at [contact] or [[contact]](mailto:[contact]).

Digitized by [contact]

Figure 1 is a bar chart showing the percentage of patients with different types of primary glioma. The y-axis is labeled 'Type of primary glioma' and the x-axis is labeled 'Percentage' with tick marks at 0, 50, and 100. There are four bars representing different tumor grades: Grade I (low grade), Grade II (intermediate grade), Grade III (high grade), and Grade IV (highest grade). The bars are black with white outlines. The approximate percentages are: Grade I (~10%), Grade II (~45%), Grade III (~30%), and Grade IV (~15%).

Type of primary glioma	Percentage
Grade I (low grade)	~10%
Grade II (intermediate grade)	~45%
Grade III (high grade)	~30%
Grade IV (highest grade)	~15%

11. **What is the primary purpose of the *Journal of Clinical Endocrinology and Metabolism*?**

## **11. APPENDICES**

## Appendix 1. Abbreviations and trademarks

Term	Definition
ADL	Activities of daily living
AE	Adverse event
ALT	Alanine Aminotransferase
ANOVA	Analysis of variance
AMD	Age-related macular degeneration
AST	Aspartate Aminotransferase
AVD-104	PSA-PLGA-nanoparticle construct
BCVA	Best-Corrected Visual Acuity
BLD	Bright-light damage
C3	Complement 3
CATT	Comparison of Age-Related Macular Degeneration Treatments Trial
CFH	Complement factor H
CFI	Complement factor I
CFR	Code of Federal Regulations
CIOMS	Council for International Organizations of Medical Sciences
CNV	Choroidal neovascularization
CRC	Central reading center
CRF	Case report form
CSR	Clinical study report
CTCAE	Common Terminology Criteria for Adverse Events
DA	Disk area
DLT	Dose-Limiting Toxicity
DMC	Data Monitoring Committee
DR	Diabetic retinopathy
DSMC	Data and Safety Monitoring Committee
eCRF	Electronic case report form
EDC	Electronic data capture
EIOP	Elevated intraocular pressure
EOM	Every other month
ERG	Electroretinogram
ETDRS	Early-Treatment Diabetic Retinopathy Study
EZ	Ellipsoid zone
FA	Fluorescein angiography
FAF	Fundus Autofluorescence
FSH	Follicle-stimulating hormone
F/U	Follow-up
GA	Geographic Atrophy
GCP	Good clinical practice
HBsAg	Hepatitis B surface antigen
hCG	Human chorionic gonadotropin
HIPAA	Health Insurance Portability and Accountability Act
HIV	Human immunodeficiency virus
HRT	Hormonal replacement therapy
IB	Investigator's Brochure
ICF	Informed consent form

Term	Definition
ICH	International Conference on Harmonization
IEC	Independent Ethics Committees
INR	International normalized ratio
IOP	Intraocular pressure
IRB	Institutional review board
ITIM	Immunoreceptor tyrosine-based inhibitory motif
IUD	Intrauterine device
IUS	Intrauterine hormone-releasing system
IVRS	Interactive Voice Response System
IVT	Intravitreal Injection
IWRS	Interactive Web Response System
MCH	Macrocytic anemia
MCV	Mean corpuscular volume
MedDRA	Medical Dictionary for Regulatory Activities
MIP-1	Macrophage inflammatory protein 1 A and B
MPO	Myeloperoxidase
MTD	Maximum Tolerated Dose
NCI	National Cancer Institute
NET	Neutrophil extracellular trap
NHP	Non-human primate
OCT	Optical Coherence Tomography
PEG	Polyethylene glycol
PD	Pharmacodynamics
PLGA	Poly (D, L-lactic-co-glycolic acid)
PMA	Phorbol myristate acetate
PSA	Polysialic acid
q	Quisque (every)
ROS	Reactive oxygen species
RP2D	Recommended Phase 2 dosing
RPE	Retinal pigment epithelium
SAE	Serious adverse event
SD-OCT	Spectral-Domain Optical Coherence Tomography
SGOT	Serum Glutamic-Oxaloacetic Transaminase
SGPT	Serum Glutamic-Pyruvic Transaminase
SHP-1	Src homology region 2 domain-containing phosphatase-1
SoA	Schedule of Activities
SUSAR	Suspected unexpected serious adverse reactions
TEAE	Treatment emergent adverse event
ULN	Upper limit of normal
VA	Visual Acuity
VAS	Visual Acuity Scale
VEGF	Vascular endothelial growth factor
WBC	White blood cell
WOCBP	Women of childbearing potential
YAG	Yttrium aluminum garnet

## Appendix 2. Clinical laboratory tests

- The tests detailed in [Table 3](#) will be performed by the central laboratory, except as noted below.
- Local laboratory results are only required in the event that the central laboratory results are not available in time for either study treatment administration and/or response evaluation. If a local sample is required, it is important that the sample for central analysis is obtained at the same time. Additionally, if the local laboratory results are used to make either a study treatment decision or response evaluation, the results must be entered into the CRF.
- Protocol-specific requirements for inclusion or exclusion of participants are detailed in [Section 5](#) of the protocol.
- Additional tests may be performed at any time during the study as determined necessary by the investigator or required by local regulations.

**Table 3: Protocol-Required Safety Laboratory Assessments**

## Appendix 3. Study governance considerations

### Regulatory and ethical considerations

- This study will be conducted in accordance with the protocol and with:
  - Consensus ethical principles derived from international guidelines including the Declaration of Helsinki and Council for International Organizations of Medical Sciences (CIOMS) International Ethical Guidelines
  - Applicable ICH Good Clinical Practice (GCP) Guidelines
  - Applicable laws and regulations
- The protocol, protocol amendments, ICF, Investigator Brochure, and other relevant documents (eg, advertisements) must be submitted to an IRB/IEC by the investigator and reviewed and approved by the IRB/IEC before the study is initiated.
- Any amendments to the protocol will require IEC/IRB approval before implementation of changes made to the study design, except for changes necessary to eliminate an immediate hazard to study participants.
- The investigator will be responsible for the following:
  - Providing written summaries of the status of the study to the IRB/IEC annually or more frequently in accordance with the requirements, policies, and procedures established by the IRB/EC
  - Notifying the IRB/IEC of SAE or other significant safety findings as required by IRB/IEC procedures
  - Overall conduct of the study at the site and adherence to requirements of 21 CFR, ICH guidelines, the IRB/IEC, European regulation 536/2014 for clinical studies (if applicable), and all other applicable local regulations

### Financial disclosure

Investigators and sub-investigators will provide the sponsor with sufficient, accurate financial information in accordance with local regulations to allow the sponsor to submit complete and accurate financial certification or disclosure statements to the appropriate regulatory authorities. Investigators are responsible for providing information on financial interests during the course of the study and for 1 year after completion of the study.

### Informed consent process

- The investigator or his/her representative will explain the nature of the study to the participant or his/her legally authorized representative and answer all questions regarding the study.
- Participants must be informed that their participation is voluntary. Participants or their legally authorized representative, defined as an individual or judicial or other body authorized under applicable law to consent on behalf of a prospective subject to the subject's participation in the clinical research, will be required to sign a statement of informed consent that meets the requirements of 21 CFR 50, local regulations, ICH guidelines, Health Insurance Portability and Accountability Act (HIPAA) requirements, where applicable, and the IRB/IEC or study center.
- The medical record must include a statement that written informed consent was obtained before the participant was enrolled in the study and the date the written consent was obtained. The authorized person obtaining the informed consent must also sign the ICF.
- Participants must be re-consented to the most current version of the ICF(s) during their participation in the study.

- A copy of the ICF(s) must be provided to the participant or the participant's legally authorized representative.

Participants who are rescreened are required to sign a new ICF.

Both blood and aqueous humor samples will be kept in storage for a potential exploratory analysis regarding the pathogenesis of macular degeneration and response to study treatment.

Participants will be told that they are free to refuse to participate and may withdraw their specimens at any time and for any reason during the storage period.

### **Data protection**

- Participants will be assigned a unique identifier by the sponsor. Any participant records or datasets that are transferred to the sponsor will contain the identifier only; participant names or any information, which would make the participant identifiable will not be transferred.
- The participant must be informed that his/her personal study-related data will be used by the sponsor in accordance with local data protection law. The level of disclosure must also be explained to the participant.
- The participant must be informed that his/her medical records may be examined by Clinical Quality Assurance auditors or other authorized personnel appointed by the sponsor, by appropriate IRB/IEC members, and by inspectors from regulatory authorities.

### **Publication policy**

- The results of this study may be published or presented at scientific meetings. If this is foreseen, the investigator agrees to submit all manuscripts or abstracts to the sponsor before submission. This allows the sponsor to protect proprietary information and to provide comments.
- The sponsor will comply with the requirements for publication of study results. In accordance with standard editorial and ethical practice, the sponsor will generally support publication of multicenter studies only in their entirety and not as individual site data. In this case, a coordinating investigator will be designated by mutual agreement.
- Authorship will be determined by mutual agreement and in line with International Committee of Medical Journal Editors authorship requirements.

### **Dissemination of clinical study data**

#### **Data quality assurance**

- All participant data relating to the study will be recorded on printed or electronic CRF unless transmitted to the sponsor or designee electronically (eg, laboratory data). The investigator is responsible for verifying that data entries are accurate and correct by physically or electronically signing the CRF.
- The investigator must maintain accurate documentation (source data) that supports the information entered in the CRF.
- The investigator must permit study-related monitoring, audits, IRB/IEC review, and regulatory agency inspections and provide direct access to source data documents.
- The sponsor or designee is responsible for the data management of this study including quality checking of the data.
- Study monitors will perform ongoing source data verification to confirm that data entered into the CRF by authorized site personnel are accurate, complete, and verifiable from source documents; that the safety and rights of participants are being protected; and that the study

is being conducted in accordance with the currently approved protocol and any other study agreements, ICH GCP, and all applicable regulatory requirements.

- Records and documents, including signed ICF, pertaining to the conduct of this study must be retained by the investigator for 10 years after study completion unless local regulations or institutional policies require a longer retention period. No records may be destroyed during the retention period without the written approval of the sponsor. No records may be transferred to another location or party without written notification to the sponsor.

### **Source documents**

- Source documents provide evidence for the existence of the participant and substantiate the integrity of the data collected. Source documents are filed at the investigator's site.
- Data reported on the CRF or entered in the eCRF that are transcribed from source documents must be consistent with the source documents or the discrepancies must be explained. The investigator may need to request previous medical records or transfer records, depending on the study. Also, current medical records must be available. Definition of what constitutes source data can be found in 21 CFR 312.62(b).

### **Study and site closure**

The sponsor or its designee may stop the study or study site participation in the study for medical, safety, regulatory, administrative, or other reasons consistent with applicable laws, regulations, and GCP.

## Appendix 4. Adverse events: definitions and procedures for recording, evaluating, follow-up, and reporting

### Definition of AE

#### AE Definition

- An AE is any untoward medical occurrence in a patient or clinical study participant, temporally associated with the use of a medicinal product, whether or not considered related to the medicinal product.
- NOTE: An AE can therefore be any unfavorable and unintended sign (including an abnormal laboratory finding), symptom, or disease (new or exacerbated) temporally associated with the use of a medicinal product.

#### Events Meeting the AE Definition

- Any abnormal laboratory test results (hematology, clinical chemistry, or urinalysis) or other safety assessments (eg, ophthalmic scans, vital signs measurements), including those that worsen from baseline, considered clinically significant in the medical and scientific judgment of the investigator (ie, not related to progression of underlying disease).
- Exacerbation of a chronic or intermittent pre-existing condition includes either an increase in frequency and/or intensity of the condition.
- New conditions detected or diagnosed after study treatment administration even though it may have been present before the start of the study.
- Signs, symptoms, or the clinical sequelae of a suspected drug-drug interaction.
- Signs, symptoms, or the clinical sequelae of a suspected overdose of either study treatment or a concomitant medication. Overdose per se will not be reported as an AE/SAE unless it is an intentional overdose taken with possible suicidal/self-harming intent. Such overdoses should be reported regardless of sequelae.
- "Lack of efficacy" or "failure of expected pharmacological action" per se will not be reported as an AE or SAE. Such instances will be captured in the efficacy assessments. However, the signs, symptoms, and/or Clinical sequelae resulting from lack of efficacy will be reported as AE or SAE if they fulfil the definition of an AE or SAE.

#### Events NOT Meeting the AE Definition

- Any clinically significant abnormal laboratory findings or other abnormal safety assessments, which are associated with the underlying disease, unless judged by the investigator to be more severe than expected for the participant's condition.
- The disease/disorder being studied or expected progression, signs, or symptoms of the disease/disorder being studied, unless more severe than expected for the participant's condition.
- Medical or surgical procedure (eg, endoscopy, appendectomy): the condition that leads to the procedure is the AE.
- Situations in which an untoward medical occurrence did not occur (social and/or convenience admission to a hospital).
- Anticipated day-to-day fluctuations of pre-existing disease(s) or condition(s) present or detected at the start of the study that do not worsen.

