**Definition of SAE**

If an event is not an AE per definition above, then it cannot be an SAE even if serious conditions are met (eg, hospitalization for signs/symptoms of the disease under study, death due to progression of disease).

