4 EFFICACY ANALYSES

All efficacy data will be presented as data listings except visual acuity and retinal thickness (as by OCT assessed) The data for these variables will be summarized using summary statistics by scheduled visit for each treatment group.

[figure not shown]

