5 SAFETY ANALYSES

All safety analyses will be performed using the Safety Population.

The primary safety variable is the incidence and severity of ocular and systemic AEs and SAEs. MedDRA Version 26.1 (September 2023) nomenclature will be used to code adverse events. The number and percent of participants reporting ocular and systemic AEs/SAEs will be tabulated based on the MedDRA System Organ Class and Preferred Term. Summary tables will be generated for all AEs regardless of causality as well as for treatment-related AEs.

The following safety data will be analyzed and presented in tabular format:

- Overview of Treatment Emergent Adverse Events
- Summary of Adverse Events by System Organ Class and Preferred Term
- 

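### Study-eye worsening judged to be expected progression is not an AE or SAE, and no visible planned table counts eyes that worsened regardless of that judgement

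*Protocol*

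**What the plan says.** **AE definition (Protocol Appendix 4).** Under Events NOT Meeting the AE Definition, the studied disease is excluded together with "expected progression, signs, or symptoms of the disease/disorder being studied, unless more severe than expected". Abnormal safety assessments are excluded on the same test: those "which are associated with the underlying disease, unless judged by the investigator to be more severe than expected for the participant's condition". Under Events Meeting the AE Definition, worsened safety assessments, with ophthalmic scans among the examples, count when "considered clinically significant in the medical and scientific judgment of the investigator (ie, not related to progression of underlying disease". The same list also admits a worsening pre-existing condition: "Exacerbation of a chronic or intermittent pre-existing condition includes either an increase in frequency and/or intensity of the condition".

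**SAE definition (Protocol Appendix 4).** "If an event is not an AE per definition above, then it cannot be an SAE even if serious conditions are met".

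**Endpoint.** Protocol section 4 bases the primary endpoint on examination evidence of ocular, systemic or serious adverse events. SAP section 5 states: "The primary safety variable is the incidence and severity of ocular and systemic AEs and SAEs".

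**Acuity and thickness.** SAP section 4 treats both as efficacy: "The data for these variables will be summarized using summary statistics by scheduled visit for each treatment group". SAP section 2.6 lists the statistics: n, mean, SD, median, minimum and maximum.

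**Design.** Participants are randomized between two AVD-104 regimens (Protocol 4.1.1), with 15 per group in the Schedule of Activities. The reading center and vision examiner are masked (Protocol 6.3, SAP 2.2). Vision-specific AE reporting guidelines exist in Protocol 8.5.2, but their content is redacted.

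**The concern.** In DME, a harmful effect of an intravitreal drug on the macula would look like the disease: a thicker center and fewer letters read. Inclusion criteria 7 and 8 require reduced acuity and center-involving thickening, so every study eye already has the condition that such harm would imitate.

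Whether a worsening reaches the primary endpoint then turns on one judgement, namely what was expected for that participant. The visible text gives no BCVA or CST threshold for it. No arm without AVD-104 supplies the expected course, so harm common to both regimens cannot be separated from natural progression. If worsening is called progression, it leaves the AE tables and the SAE tables together.

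At stake is the reading of a clean AE table. From that table alone, one could not tell whether no eyes worsened or whether worsening had been classed as disease.

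**Working it through.** **1. Path of a worsening study eye through the visible rules**

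| Step | Source | Result |
|---|---|---|
| Exacerbation of a pre-existing condition | Appendix 4, Events Meeting the AE Definition | AE |
| Expected progression of the studied disease | Appendix 4, Events NOT Meeting the AE Definition | Not an AE unless more severe than expected |
| Not an AE | Appendix 4, Definition of SAE | Cannot be an SAE |
| Not an AE or SAE | SAP section 5 | Outside the primary safety variable |

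The first two rows can both describe the same DME eye, so two sites could classify the same event differently.

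**2. Who decides, and against what reference**

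Measurement is masked: the vision examiner and reading center do not know the arm. Classification is a separate act by the investigator, for whom no masking is stated. The groups also have different injection visits (Days 0, 28 and 56 against Days 0 and 56), with no sham injection in the visible text. Since both arms receive AVD-104, a difference between regimens could be seen, but a shared effect could not.

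**3. What the planned summaries would show**

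Illustration only; the letter changes are assumed. In one arm of 15, two eyes lose 15 letters and the other 13 gain equally so that the mean is zero.

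- Gain per other eye: 2 × 15 / 13 = 30/13 = 2.3 letters.
- Mean change: (−30 + 30)/15 = 0. Median: +2.3.
- SD: √[(2 × 15² + 13 × 2.31²)/14] = √(519.2/14) = 6.1.
- Minimum: −15.

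The minimum reveals a 15-letter loss, provided that change is summarized. It is −15 whether one eye or two lost 15 letters, so it gives no count. If observed scores are summarized instead, even this signal is lost, because eligible scores run from 20 to 75 letters. SAP section 4 does not say which is summarized, although the BCVA endpoint is a change from baseline.

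A direct count gives 2/15 = 13.3%, with exact (Clopper–Pearson) 95% limits of 1.7% and 40.5%.

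**4. Scale of possible under-counting**

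The documents give no event rate. Let p be an assumed true rate of drug-caused worsening and c the assumed share recorded as AEs. Then P(at least one recorded) = 1 − (1 − p·c)^n.

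| n | p | c = 1 | c = 0.5 | c = 0.25 |
|---|---|---|---|---|
| 15 | 5% | 53.7% | 31.6% | 17.2% |
| 15 | 10% | 79.4% | 53.7% | 31.6% |
| 15 | 20% | 96.5% | 79.4% | 53.7% |
| 30 | 10% | 95.8% | 78.5% | 53.2% |

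Zero recorded events gives a one-sided 95% upper bound of 1 − 0.05^(1/n): 18.1% for 0/15 and 9.5% for 0/30. These bounds hold only if every case is recorded (c = 1).

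The plan has no figure to reproduce on this point beyond 15 + 15 = 30, which agrees with planned enrollment.

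**The case against.** The strongest reply is that the decisive text is hidden. Protocol 8.5.2 sets out how vision problems are reported as possible AEs. If it names a reportable loss, that loss enters the System Organ Class and Preferred Term table and is counted. The visible list of safety tables in SAP section 5 ends in an empty bullet, SAP section 4 ends in a figure not shown, and the rescue criteria and Protocol section 9 cannot be read. This stands: neither actual drop-out of vision loss nor the absence of a vision-loss table can be confirmed.

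Other counterweights stand in part. Exacerbation is listed as an AE. The intensity scale defines its life-threatening grade by threatened loss of vision or the eye, so serious visual events are plainly expected in AE reporting. An event more severe than expected still qualifies as an AE, and can then be an SAE. SAP section 3.1 puts all data in listings, although SAP section 4 appears to except visual acuity and thickness. Listings hold individual values but give no prespecified count.

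A reader might infer more than the documents support:

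- **That the study is unmasked and uncontrolled.** Those who measure acuity and read images are masked, and the trial is randomized between regimens. What is missing is an arm without AVD-104 and any stated masking of the classifying investigator.
- **That individual losses would be invisible.** The planned minimum can show the worst eye; the number of eyes is what is lacking.
- **That the safety conclusion is biased.** The text supports a conditional risk, not a demonstrated bias.

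**Conclusion.** The point holds as a risk of under-counting, with a cheap remedy. On the visible rules, study-eye worsening attributable to the drug could be classed as expected progression and so be missing from the AE-based primary endpoint. The measurements are not lost: acuity and thickness are still summarized, but as efficacy, and the visible summaries do not count worsening eyes.

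The size cannot be estimated from the documents. Under the assumptions p = 10% and n = 15, recording half of the cases lowers the chance of seeing any from 79.4% to 53.7%. For vision loss, the conclusion depends on the redacted content of Protocol 8.5.2. The case for a count independent of AE classification does not depend on that content, unless hidden text already provides one.

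**What to change.** Unless redacted text already provides it, add one descriptive table to SAP section 5, on the Safety population and regardless of AE classification. Give number and percent per arm, by visit and at any visit, for:

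- study-eye BCVA loss from Day 0 of at least 5, 10 and 15 letters, with exact 95% CIs;
- study-eye CST increase from Day 0 above a threshold fixed before analysis;
- participants who received rescue treatment.

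State the denominators, because SAP section 2.5 rules out imputation: for example, participants with a Day 0 value and a value at that visit, or with at least one later value for the any-visit row.

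Reconcile, for the study eye, the Appendix 4 entry on exacerbation of a pre-existing condition with the entry on expected progression, and state in the SAP how the more-severe-than-expected test is applied.

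The cost is one table and short clarifying text. No visit or measurement is added: BCVA and SD-OCT are already scheduled at Days 0, 28, 56 and 84. The downside is that some counted losses will be natural progression, which the table cannot separate from drug effect, and that intervals are wide at about 15 per arm. The table should be labelled descriptive and read beside the AE tables.
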